		1.1. Revision Date(s) add rows as needed

Title: Randomized controlled trial of wound healing following tooth extraction and ridge preservation using demineralized freeze-dried bone allograft (DFDBA) in cortical particulate form versus fiber form

2. Background

Briefly discuss the important literature relevant to the trial and that provides background for the trial. Include the importance of the trial and any relevant treatment issues or controversies.

Bone grafting following tooth extraction is performed to preserve bony ridge dimensions adequate to allow subsequent implant placement in a proper restoratively-driven position. Alveolar ridge resorption commonly occurs following tooth extraction, and the decrease in bone volume has the potential to make dental implant therapy impossible without surgery to reconstruct the ridge. The aim of ridge preservation grafting is to prevent or minimize this resorptive process, thereby preserving satisfactory bone volume for implant placement, while also obtaining an adequate amount of new vital bone formation to support implant integration. Ridge preservation generally involves placement of a bone graft material in the tooth socket, followed by use of a membrane or wound dressing over the socket entrance to contain the bone graft.

Various grafting materials have been recommended for ridge preservation procedures, including cortical and cancellous freeze-dried bone allograft (FDBA), demineralized freeze-dried bone allograft (DFDBA), and various xenografts, alloplasts and autografts. Our research group in the Department of Periodontics at the UT Health San Antonio School of Dentistry has spent over 15 years evaluating wound healing and clinical changes in ridge dimension following ridge preservation procedures using a variety of bone grafting materials and treatment protocols.¹⁻¹⁹ In many of these studies, bone allografts were used for ridge preservation^{2,3,5,8-13,15-19}, while in others xenograft was used.^{4,14} Our research has generally involved the histologic evaluation of wound healing after ridge preservation as the primary outcome measure, with the main parameters of healing being the percentage of new vital bone formation, residual bone graft material and connective tissue/other (CT/other) non-bone material at the ridge preservation site. We have used different bone replacement graft materials, wound barriers, and regenerative membranes to discern any differences in wound healing with numerous techniques at various time points after ridge preservation. Our studies have also evaluated clinical or radiographic changes in ridge dimension (vertical ridge height and horizontal ridge width changes) as secondary outcomes.

In two studies, we compared 100% cortical mineralized FDBA, 100% cancellous mineralized FDBA and a combination of 50% cortical with 50% cancellous mineralized FDBA and found no significant difference in new bone formation between groups at 18 to 20 weeks post-ridge preservation.^{5,12} Because demineralized FDBA has been used in periodontics for decades, Wood & Mealey³ compared demineralized FDBA to mineralized FDBA for ridge preservation and found significantly greater vital bone with DFDBA formation (38.4%) compared to mineralized FDBA (24.6%) at 18 to 20 weeks post-ridge preservation. Due to these positive outcomes with DFDBA, Whetman & Mealey⁹, then examined earlier healing time points after ridge preservation using DFDBA. An average of 47% vital bone was found at 18 to 20 weeks of healing, but as early as 8 to 10 weeks after grafting, 32% vital bone was already present.

Over the past several years, combination allografts that include both mineralized and demineralized FDBA have become available, and our study group has evaluated these materials in several randomized controlled clinical trials. Borg and Mealey⁸ used a combination allograft (70% FDBA:30% DFDBA) compared to 100% FDBA and found greater vital bone formation in the 70%:30% group (36%) compared to FDBA alone (24%) at 18 to 20 weeks of healing. The robust vital bone formation found with the 70% FDBA:30% DFDBA combination allograft led to a study evaluating healing at earlier time points. Nelson and Mealey¹² found that using a combination allograft of 70% FDBA:30% DFDBA resulted in 18% vital bone at 8 to 10 weeks, compared to 40% vital bone at 18 to 20 weeks, over twice the amount of vital bone formation with a longer healing time.

Systematic reviews and meta-analyses have examined ridge dimensional changes following ridge preservation procedures.^{20,21} Our study group also evaluates changes in ridge dimension in each of our studies using various materials and protocols for ridge preservation.

Recently, non-particulate allograft products have become available for use in periodontal, implant, and oral surgical procedures. Most of these materials have little human wound healing data when they are used for ridge preservation after tooth extraction. In addition, there few published studies of wound healing results after ridge preservation performed combinations of xenograft and allograft materials.

References:

3.1. Objective(s) Clearly and concisely define the primary and secondary outcomes.	3.2. Endpoint Clearly define the endpoints. (endpoints are the basis for concluding that the objective has been met).	3.3. Justification for Endpoint Briefly explain why the endpoint(s) were chosen.
Primary Histologic Outcome	% vital bone formation	% vital bone formation shows the amount of new bone formed after the procedure. The higher this % is the better the healing of the site
Secondary histologic outcomes	% residual graft material, and % "CT/other" (fibrous tissue and marrow space)	% residual graft material shows how much of the graft material remained intact. Ideally all the graft materials should turn over to vital bone % CT/other (fibrous tissue and marrow space) is the amount of tissue that is neither native bone or graft material. It may be connective tissue that will mature to osteoid and bone or marrow space that is part of the normal healing
Secondary Clinical outcomes	Change in ridge width; Change in buccal ridge height; Change in lingual ridge height	Clinical measurements show effects of procedures on dimensional changes in the alveolar ridge during healing

4. Rationale

Briefly state the reason for conducting the clinical trial.

Allografts and xenografts are commonly used in ridge preservation procedures. Demineralized freeze-dried bone allografts (DFDBA) are available in particulate and fibers forms. Newer products on the market combine xenografts and DFDBA, but there are little data on histologic healing. Our group is known for this type of research, and we wish to determine if DFDBA fibers result in similar or different histologic outcomes than DFDBA particulate, and whether bovine-derived xenograft combined with DFDBA fibers result in similar or different histologic outcomes than xenograft combined with DFDBA particulate. Finally, we will be able to assess histologic outcomes when particulate DFDBA is used alone versus when it is combined with xenograft and when DFDBA in fiber form is used alone versus when it is combined with xenograft.

5. Study Design

5.1. Number of Groups/Arms	4	Group name(s)	
 1. Group 1: DFDBA particulate at 125-850 micron size (Vallos) 2. Group 2: Xenograft (Bio-Oss) combined with DFDBA particulate at 125-850 micron size (Vallomix) 3. Group 3: DFDBA fibers (Vallos-F)
-----------------------------------	---	----------------------	---

			4. Group 4: Xenograft (Bio-Oss) combined with DFDBA fibers (Vallomix-F)			
5.2. Overall Design Select all applicable						
	Randomization					
	Group-Sequential					
	Parallel Design					
	Superiority					
Device		Pilot				
		Pivotal				
			Post-Approval			
Drug/Biologic	Phase 1	Phase 1/2	Phase 2	Phase 2/3	Phase 3	Phase 4
Dose escalation	If yes, details →					
Dose ranging	If yes, details →					
Sub-studies	If yes, details →					
5.3. Other Design Details: This protocol summary is for a study entitled, " A 4-arm randomized controlled trial of wound healing following tooth extraction and ridge preservation using DFDBA alone in particulate or fiber form, and in combination with xenograft. " The primary aim of the study is to determine the amount of newly formed vital bone, residual graft material, and "connective tissue/other" 18 to 20 weeks after ridge preservation is performed using DFDBA fibers alone, DFDBA particulate alone, a combination of xenograft and DFDBA particulate, or a combination of xenograft and DFDBA fibers. The study only involves use of these FDA-approved materials in an FDA-approved manner (for ridge preservation).						
The study is a 4-arm, parallel-design, randomized, prospective clinical trial. The study is designed to examine histologic wound healing 18 to 20 weeks following ridge preservation. The study arms include: 
 1. Group 1: DFDBA particulate at 125-850 micron size (Vallos) 2. Group 2: Xenograft (Bio-Oss) combined with DFDBA particulate at 125-850 micron size (Vallomix) 3. Group 3: DFDBA fibers (Vallos-F) 4. Group 4: Xenograft (Bio-Oss) combined with DFDBA fibers (Vallomix-F) 						
The patient and the individual doing histomorphometry will be blinded as to study group allocation. The surgeon cannot be blinded in this study.						
Null hypothesis: There will be no significant between-group difference in vital bone formation after ridge preservation.						
Based on power analysis and drop-out experience from previous studies, we plan to ask our IRB for approval to enroll 30 patients in each of the 4 study groups, with a total of 120 patients for the 4 study groups combined.						
All of the bone graft material and overlying membrane material will be provided by Geistlich Biomaterials. To eliminate variability that might occur if more than one human donor's tissue is used in the study, all of the DFDBA graft material for all treatment groups will be derived from a single human donor. The DFDBA graft material will be tested for inductivity by the tissue bank (DCI Donor Services Tissue Bank).						
All patients will have a single non-molar tooth extracted. Following extraction, patients will be randomized to one of the 4 treatment groups. Clinical ridge measurements will be made using a custom-made thermoplastic measurement stent, and ridge preservation will be performed using one of the materials listed above, per assigned study arm. After graft placement, the graft material will be covered with a resorbable collagen membrane (Bio-gide) membrane (Geistlich Biomaterials) and the site will be sutured with resorbable sutures without attempt at primary closure.						
Patients will return 1 to 3 weeks after ridge preservation for post-operative evaluation, and thereafter as indicated by clinical findings. Following the 18 to 20-week wound healing period, a core biopsy will be harvested from the site at the time of implant placement. Just prior to the core biopsy, clinical ridge measurements will again be made using the customized measurement stent.						
The core biopsy will be evaluated histomorphometrically for the primary outcome: % vital bone formation. Secondary histologic outcomes include % residual graft material and % "CT/other" (fibrous tissue and marrow space). The histomorphometric						

evaluation will be performed blindly, as the cores being examined will be de-identified as to study arm. In line with our other studies, we will also evaluate the following **secondary clinical outcomes** for each subject: change in ridge width; change in buccal ridge height and change in lingual ridge height.

DETAILED DESCRIPTION OF METHODS:

In keeping with the protocol our study group has used numerous times before, the plan is to extract non-molar teeth and graft with the various graft materials. Each subject will provide a single non-molar tooth site for study treatment. Following approx. 18-20 weeks of healing, we will harvest a core biopsy at the time of implant placement. The implant osteotomy is prepared with a trephine drill and the core inside the trephine is placed in 10% formalin for future processing and histomorphometric analysis. The core biopsy will be evaluated for the primary histologic outcome of % vital bone formation and the secondary histologic outcomes of % residual graft material, and % "CT/other" (fibrous tissue and marrow space). We will also evaluate the following secondary clinical outcomes using a custom measuring stent for each subject: change in ridge width; change in buccal ridge height and change in lingual ridge height. During the 18 to 20-week healing period, patients will be followed as needed per standard care to evaluate healing.

A detailed visit by visit outline is provided below:

Step-by-Step Methods: All the procedures are routinely performed in the graduate periodontics clinic as part of standard care. The methodology is the same previous studies of our group HSC20130470H, HSC20150708H, HSC20170339H, HSC20170267H, HSC2019-0455H, among others.

Visit 1 - Screening examination:

If a patient presents at a consultation appointment at the graduate periodontics clinic with a non-molar tooth (incisors, canines, premolars) that needs to be extracted and replaced with a dental implant, the treating doctor will provide:

- Explanation to the patient of the purposes of the study and the planned procedures related to the study.
- Explanation to the patient of the risks, benefits and possible complications of participation in the study.
- Notification to the patient that inclusion in the study is voluntary and that they will still receive standard of care treatment if they choose not to participate, and conditional upon satisfying the inclusion and exclusion criteria.

Patients will be given the opportunity during the appointment to ask any question that they may have. Following an informational discussion with the prospective subject, consent will be obtained within 2 weeks. This is up to the discretion of the patient. If the patient would like to become a subject for entry into the study, he or she can do so immediately, or can consider it for up to 2 weeks (must be prior to extraction).

Visit 2 – Extraction with ridge preservation using one of the 4 materials described above. All materials are FDA approved and will be used in an FDA approved manner. If the patient has agreed to participate in the study, informed consent will be obtained and documented on a written consent form. If not, standard care treatment will be provided to the patient, and the patient would not be included in the study. Patients will be assigned to one of the 4 groups by randomization with a 1:1 ratio.

On the day of the planned tooth extraction, the medical history will be updated.

Pregnant women or women intending to become pregnant during the study period: Prior to dental surgery, females of child-bearing age are asked verbally if there is any possibility that they are pregnant. If not, we proceed with surgery and no pregnancy test is done. If the woman states that there is a possibility that she is pregnant, an over-the-counter urine pregnancy test to rule pregnancy in or out will be provided. Use of the urine pregnancy test is only done if she says she may be pregnant. [If needed: Urine pregnancy test will be provided to female subjects in the graduate periodontics clinic of UTHSCSA and a negative result is required to enter the study.]

Prior to extraction, impressions of the arch with the tooth to be extracted in place will be taken and poured in stone to obtain initial study casts (research). A clear suck-down resin measuring stent will be fabricated in the laboratory to allow standardization of the location of clinical measurements of ridge width and height through small holes that will be placed in the stent at the time of tooth extraction.

A pre-operative periapical radiographic image will be taken before the extraction as per standard care (if not already available).

At the time of surgery, local anesthesia will be administered. Conscious sedation will be administered according to patient need and investigator preference, per standard care. Buccal and lingual flaps will be minimally reflected to a point up to 3mm apical to

the bony crest. Prior to tooth extraction, the clinical measurement stent will be placed and measurements of ridge width and ridge height will be taken and recorded to the nearest 0.5mm. Ridge width will be measured to the nearest 0.5mm using a ridge caliper at a point **approximately 3mm apical to the facial and lingual bony crest** through small holes created in the stent at those locations. Ridge height will be measured to the nearest 0.5mm through two holes in the occlusal aspect of the stent – one hole directly above the facial bony crest and another hole directly above the lingual bony crest. This stent will be retained for use during the subsequent implant placement surgery.

Use of the stent and subsequent measurements are for research purposes, not standard care.

Tooth extraction will be performed as atraumatically as possible. Following tooth extraction, a final determination of enrollment into the study will be conducted based on the integrity of the buccal bone wall plate at the extraction site. If the buccal plate is intact, defined as **no bony dehiscence greater than 50% of the socket depth**, the patient will remain enrolled in the study. Conversely, if the buccal plate integrity has not been maintained (bony dehiscence >50%) the patient will be exited from the study and standard care therapy will be delivered to the patient.

After extraction, the number of bony walls in each socket will be recorded along with the presence of any bony dehiscences or fenestrations. Buccal and lingual flap elevation will be minimized and will extend no more than 2-3mm beyond the bony crest on the facial and lingual surfaces. The buccal plate thickness will be measured using an Iwanson gauge positioned perpendicular to the inner wall of the extraction socket. One beak of the gauge will be placed within the extraction socket 1.0mm apical to the alveolar bone crest. The other beak will be placed on the external bone surface 1.0mm apical to the alveolar bone crest. This buccal plate thickness measurement will be recorded to the nearest 0.1 mm. Measurements taken with the Iwanson gauge are for research purposes, not standard care.

The socket will be thoroughly debrided, the patient will be randomized to one of the study groups (Group 1, 2, 3 or 4), and the graft material will be placed in the extraction socket to a level even with the interproximal bone height of the mesial and distal aspects of the socket. The material will be condensed into the socket gently. In all sockets, a BioGide resorbable collagen membrane will be placed over the socket and graft material to retain the material in place. The edges of the membrane will be “tucked” under the flap margins to help with membrane retention, and the flaps will be sutured. Primary closure of the flaps will not be performed, per standard care. Flaps will be stabilized with chromic gut sutures, per standard care.

Visit 3 - Post-operative visit

The post-operative visit after extraction/ridge preservation will be scheduled approximately 3 weeks (± 1 week) after the procedure. At this visit a clinic exam will be performed to evaluate healing. Any remaining sutures will be removed. If needed, an optional POT visit may be scheduled before this visit, per standard care and as determined by patient need.

Visit 4 - Pre-implantation:

Approximately 3-4 months after the extraction, the patient will be seen for pre-implant evaluation, per standard care. If needed, a cone beam computed tomography (CBCT) scan will be taken per standard care.

Prior to surgery, pregnancy status will be confirmed verbally. An over-the-counter pregnancy test will be provided if pregnancy status is unknown or suspected (research). A negative result is required to continue being in the study.

Visit 5 - Implant placement:

Prior to surgery, pregnancy status will be confirmed verbally. An over-the-counter pregnancy test will be provided if pregnancy status is unknown or suspected (research). A negative result is required to continue being in the study.

The implant surgery will be performed (standard care) at a time point 18 to 20 weeks after tooth extraction/ridge preservation (± 2 weeks). Per standard care, after local anesthesia (and conscious sedation if requested), the patient will undergo implant placement surgery at the previously extracted tooth site and if required simultaneous guided bone regeneration (GBR) will be performed as per standard care. First, the individual subject's measuring stent and caliper will be used to determine the ridge width and ridge height at the same locations as done in the tooth extraction/grafting surgery visit and all measurements will be documented for research purposes. During the implant bed preparation, a hollow drill will be used to allow retrieval of a bone core which will be collected and stored in formalin and subsequently examined histologically and outcomes including percentages of new bone formation, residual graft and connective tissue/other will be recorded. (Drilling procedure is per standard of care, collection of normally discarded bone core for analysis is a research procedure).

During the implant placement procedure, the following data will be recorded per standard care:

- Absence/Presence of bone defect, including dehiscence or crater like defect. If present, at what site(s) (Buccal, Mesial, Lingual, Distal) and what are the respective depth and width of these defects.

- Absence/Presence of bone fenestration. If present what is the size of the fenestration in height and width.
- Bone quality according Lekholm and Zarb (1985) classification
- Was additional bone grafting needed in case of thin bone or dehiscence of threads? Yes/No

Subject participation ends at the time of implant placement. However, standard care post-operative visits will be provided after implant placement. Generally, one or two post-operative visits will be provided during the first month after implant surgery to insure adequate healing.

6. Study Population

6.1. Study Population(s) Label/Name	6.2. Identify the criteria for inclusion The criteria that every potential participant must satisfy, to qualify for study entry.	6.3. Identify the criteria for exclusion The characteristics that make an individual ineligible for study participation.

To add more populations – select a row, copy & paste
 
Dental patients needing extraction of a non-molar (“single-rooted”) tooth and ridge preservation
	
All individuals in this study population must meet all of the inclusion criteria in order to be eligible to participate in the study
	
All individuals in this study population meeting any of the exclusion criteria at baseline will be excluded from study participation.

	
 • English-speaking patients aged 18 to 90 • One tooth, excluding molars, that has been identified by dental faculty as requiring a single tooth extraction • A dental implant is indicated and treatment planned to replace the missing tooth • Have adequate restorative space for a dental implant-retained restoration • Have at least 10mm of alveolar bone height, without impinging on the maxillary sinus or inferior alveolar canal. • Have a dehiscence of the buccal or lingual bony plate of the tooth socket extending no more than 50% of the total depth of the socket. • Female patients who have undergone a hysterectomy, tubal ligation, or menopause, and non-pregnant women of child-bearing potential. • Are nonsmokers or former smokers. Current smokers may be included if they smoke ≤10 cigarettes per day 	
 • Will not cooperate with the follow-up schedule. • Patients will not be entered who are mentally incompetent, prisoners, or pregnant. • Pregnant women or women intending to become pregnant during the study period (as confirmed verbally; an over the counter pregnancy test will be provided if pregnancy status is unknown or suspected). • Patients who become pregnant during the study will be withdrawn and standard care will be delivered. • Smokers who smoke >10 cigarettes per day • Clinical and/or radiographic determinations which will preclude inclusion in this study are: Active infection other than periodontitis; Inadequate bone dimensions or restorative space for a dental implant; Presence of a disease entity, condition or therapeutic regimen which decreases probability of soft tissue and bony healing, e.g., poorly controlled diabetes, chemotherapeutic and immunosuppressive agents, autoimmune diseases, history of bisphosphonate use or long-term steroid therapy; Positive medical history of endocarditis following oral or dental surgery.

6.4. Will screen failures be allowed to re-screen at a later date?
	 No  X  Yes If yes, describe criteria below ↓	
A patient who fails screening for a given tooth extraction may become eligible in the future should the patient require extraction of a different tooth

7. Study Intervention(s) being tested or evaluated

This can include prevention, diagnostic or therapeutic interventions (e.g., drug or device) or educational, health services or basic science interventions (e.g., educational program, health care delivery model, or examining basic physiology)

Ridge preservation with one of 4 different materials (devices):

Group 1: DFDBA particulate at 125-850 micron size (Vallos)

Group 2: Xenograft (Bio-Oss) combined with DFDBA particulate at 125-850 micron size (Vallomix)

Group 3: DFDBA fibers (Vallos-F)

Group 4: Xenograft (Bio-Oss) combined with DFDBA fibers (Vallomix-F)

8. Protocol-Directed procedures, items, services or tests

List all procedures directed by the study plan - including items or services provided as part of routine or conventional care and those needed to diagnosis or treat research related complications.

Important Note – The protocol directed procedures listed must match those in the Schedule of Activities (attachment)

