Randomization of subjects is done through use of envelopes inside which is a piece of paper with the group to which the subject will be assigned. 30 envelopes will be prepared for each of the 4 groups. The envelopes will be sealed and shuffled. The faculty staffing the procedure will draw an envelope from the stack prior to the surgical procedure appointment. Since the outcome of the study is the histologic healing, blinding of the surgeon is not necessary.
Blinding is performed only for histomorphometric measurements. The person doing histomorphometric analysis is blinded as to study group.
10.2. Study Intervention Compliance Define how adherence to the protocol (e.g., administration of study intervention, use of device,) will be assessed, and verified (if applicable, e.g., plasma assays, electronic monitoring devices, daily diaries).
Patients will need to be present at each scheduled visit. Failure to attend visits will result in exit from the study. All providers placing study materials as part of the study intervention will be trained and provided with detailed instructions to ensure methods are consistent and in compliance with the protocol. All faculty staffing residents are familiar with the study protocol and can verify the results of the procedure and measurements taken.
10.3. Permitted Concomitant Therapy This section should be consistent with the medication restrictions in the inclusion/exclusion criteria previously listed. Describe how allowed concomitant therapy might affect the outcome (e.g., drug-drug interaction, direct effects on the study endpoints).
N/A
10.4. Rescue Medicine List all medications, treatments, and/or procedures that may be provided during the study for "rescue therapy" and relevant instructions.
N/A, no rescue medicine

11. Study Intervention Discontinuation
11.1. Discontinuation of Study Intervention Describe the criteria for discontinuing the study intervention (e.g., halting rules), including any monitoring test(s) and associated clinical decision point(s). Include reasons for temporary discontinuation of the study intervention (e.g., type and quantity of adverse events), clearly stating the length of time, if applicable, and describe the data to be collected at the time of study intervention discontinuation and approaches for restarting administration of or re-challenging with study intervention.

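### The plan gives three different orders for baseline ridge measurement, extraction and allocation, so the baseline of the three secondary ridge outcomes could be read with the arm known

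*Combined protocol and SAP*

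**What the plan says.** Section 3 lists three secondary clinical outcomes: "Change in ridge width; Change in buccal ridge height; Change in lingual ridge height". Each needs a baseline and a second reading at implant surgery. Section 5.3 (Visit 5) takes the second reading with the same stent, measuring "ridge width and ridge height at the same locations as done in the tooth extraction/grafting surgery visit". Readings are made by hand and recorded to 0.5 mm.

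Three places describe how the baseline reading, the extraction or the allocation are ordered:

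- Section 5.3, design summary: "Following extraction, patients will be randomized to one of the 4 treatment groups. Clinical ridge measurements will be made". Grafting follows in the same sentence as the measurements.
- Section 5.3, Visit 2: "Prior to tooth extraction, the clinical measurement stent will be placed and measurements of ridge width and ridge height will be taken". Extraction and a check of the buccal plate come next, and then "The socket will be thoroughly debrided, the patient will be randomized to one of the study groups".
- Section 10.1: the faculty member supervising the procedure is to "draw an envelope from the stack prior to the surgical procedure appointment".

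On blinding, Section 5.3 states "The surgeon cannot be blinded in this study" and Section 10.1 states "Blinding is performed only for histomorphometric measurements". No section names a blinded examiner for the ridge readings.

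**The concern.** A change score is only as well defined as its baseline. A reading before extraction and a reading after it define different quantities, because the later one leaves out whatever the extraction itself does to the ridge. Separately, an operator who knows the arm may be influenced by it when rounding a hand reading, and any shift in the baseline passes in full into the change.

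These are formal comparisons: Section 12.1(b) states a null hypothesis on ridge dimensions, and Section 12.4 applies ANOVA to the clinical parameters. A baseline missed before extraction cannot be recovered once the tooth is out.

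**Working it through.** The plan states no figure on this point, so there is none to reproduce. The check is to set the three accounts side by side.

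| Source | Order given | Baseline before extraction? | Could the arm be known at baseline? |
|---|---|---|---|
| 5.3, design summary | extraction, randomization, ridge measurement, graft (by sentence order) | No | Yes |
| 5.3, Visit 2 | ridge measurement, extraction, buccal-plate check, debridement, randomization, graft | Yes | No |
| 10.1 | envelope drawn, then surgical appointment | Not addressed | Yes, if the envelope is opened before the reading |

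1. Taken alone, the Visit 2 order is sound: the baseline precedes both the extraction and the allocation.

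2. Combined with Section 10.1, that protection is no longer assured. An envelope drawn before the appointment allows the arm to be known at baseline even if the Visit 2 measurement step is followed exactly. Correcting the design summary alone would therefore not close the gap.

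3. No other safeguard covers the reading. The surgeon is unblinded, and Section 10.1 limits blinding to histomorphometry.

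4. Effect on one patient. Let B be the true baseline, F the reading at implant surgery and d an error in the baseline. The recorded change is F − (B + d) = (F − B) − d. With d equal to one recording step, 0.5 mm, that patient's change moves by 0.5 mm. The documents give no expected ridge change and no standard deviation for it, so this cannot be set against an effect size.

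5. Effect of mixed timing. In both Section 5.3 accounts, randomization follows extraction. Whether a patient had a pre-extraction reading is then settled before the arm is assigned, so timing cannot depend on the arm except by chance. The expected between-arm difference from mixed timing is zero. What remains is added variability and two definitions of change in one analysis.

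6. Primary outcome. Percent vital bone comes from a single core at implant surgery and is read blind. It has no baseline and is not touched.

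**The case against.** The best defence is that the conflict within Section 5.3 is only implied. In the summary the opening phrase attaches to the randomization, and the sentence on measurement has no word such as then or after. The detailed steps that follow are explicit and place the reading before extraction, so operators would probably follow them. Section 10.2 adds that providers will be trained and given detailed instructions, and that faculty can verify the measurements. This stands as far as it goes: a baseline that differs between patients is a possibility, not an expectation. It does not answer Section 10.1, which conflicts with Visit 2 on when allocation happens.

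Two stronger readings are tempting, and the documents support neither.

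- A reader might infer a between-arm bias of, say, 0.25 mm, by assuming that half of one arm and none of another is measured after extraction with a 0.5 mm shift (0.5 × 0.5 mm). Both inputs are invented. With randomization after extraction the imbalance would have to arise by chance: for two arms of 30 with 15 of the 60 patients measured late, the probability that all 15 fall in one named arm is C(30,15)/C(60,15), about 3 in a million. An envelope opened early would remove that protection, but nothing in the documents suggests that timing would then differ by arm.
- A reader might infer from Section 10.1 that the arm is known at baseline. The section says when the envelope is drawn. It does not say when it is opened, and no section says whether the person taking the reading sees it.

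**Conclusion.** The inconsistency is real and should be resolved before enrolment. Three accounts give three orders, and under two of them an unblinded operator could know the arm when reading the baseline of all three secondary clinical outcomes. If the design summary were followed, the baseline would also exclude any change caused by the extraction.

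The supportable size is limited: 0.5 mm in a patient's change for each rounding step, no quantifiable between-arm bias, and noise plus a blurred definition of change from mixed timing. The risk of reading with the arm known rests mainly on Section 10.1 and assumes that the envelope may be opened, or its content known, before the reading. The conclusion on mixed timing assumes that allocation is revealed after extraction, as both Section 5.3 accounts have it. Conclusions on % vital bone do not depend on this point.

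**What to change.** Bring the design summary and the Visit 2 randomization step in Section 5.3, and Section 10.1, to one order, built on the Visit 2 measurement step:

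1. Record ridge width and buccal and lingual height through the stent before extraction.
2. Extract, and complete the buccal-plate check that decides whether the patient stays in the study.
3. Open the sealed envelope only when the baseline is recorded and that check is passed. Section 10.1 should separate drawing from opening and say that the envelope stays sealed until then.

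Add the time of the baseline reading and the time of envelope opening to the form. Flag any baseline taken out of this order and report the number by arm.

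The cost is a few sentences of text, one added form entry and opening the envelope during the procedure. No measurement is added. The change does not blind the reading at implant surgery, for which the plan also states no blinding; that limitation should be acknowledged when the ridge outcomes are reported.
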